Protocol & Statistical Analysis Plan

Official Title: Influence of Exercise on Neurocognitive Function in Breast Cancer

NCT02793921

Document Date: 6/14/2023

Title of study:

Exercise Program in Cancer and Cognition (EPICC)

Brief description:

This is a single-site randomized control trial to test whether a moderate-intensity aerobic exercise intervention can prevent cognitive decline in postmenopausal women with breast cancer. Women who meet the eligibility criteria will be randomly assigned to either receive the intervention or usual care. Data will be collected prior to initiating endocrine therapy for breast cancer (TP1) and approximately 7 months later (TP2) and include fitness testing and a battery of neuropsychic tests, blood biomarkers, and other behavioral measures; a subset of women will undergo MR imaging. For women who agree to additional follow-up, data will also be collected approximately 12 months post TP1 (TP3).

Specific aims:

We will examine whether a well-controlled and monitored site-based exercise intervention improves cognitive function in postmenopausal women with early stage breast cancer. 1. Compared to usual care, examine whether the 6-month exercise intervention improves cognitive function in postmenopausal women with early stage breast cancer. Hypothesis 1. Exercise will improve cognitive function in women receiving AI therapy in a domain specific fashion such that attention, executive and memory functions will be influenced more than other domains.

2. Compared to usual care, examine the direct effects of exercise on neuroimaging metrics of brain health including regional gray matter volume, white matter architecture and functional dynamics of the brain and the pro-inflammatory biomarkers (IL-6, TNF- α), and explore the direct effects of exercise on symptoms (fatigue, sleep problems, depression, anxiety). Hypothesis 2. Exercise will improve neuroimaging metrics of brain health and pro-inflammatory biomarkers.

3. Compared to usual care, explore whether the effects of exercise on cognitive function are mediated by a) neuroimaging metrics of cognitive function, b) IL-6 and TNF- α levels, c) symptoms (fatigue, sleep problems, depression, anxiety), d) and moderated by E2 levels over the first six months of AI therapy.

Inclusion criteria:

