
populations and therefore submaximal vo_2 is often the desired method. This method has people walk at a slow - moderate pace with increasing grade increments up to the goal heart rate of 85% of the age-based maximum (220-age) or a rating of perceived exertion equal to or greater than 15 for those individuals whose heart rate response is blunted due to medication. This approach does not require the attendance of a physician because it is within the safe heart rate work zones and leads do not have to be attached to the participant. The submaximal vo_2 assessment usually takes about 15 - 30 minutes to complete depending on the starting fitness level of the participant. During the exercise test, heart rate is continuously monitored along with blood pressure readings every two minutes. The blood pressure is obtained by the Sentech Tango 2 automated unit. This blood pressure unit is designed for exercise testing and has been tested as a valid and reliable system to measure blood pressure during exercise. When the subject reaches the endpoint goal of the exercise test, the mouthpiece and head gear will be removed and they will undergo a four minute active cool-down in which they will walk at a slower rate with zero incline grade. After these four minutes the participant will be helped off of the treadmill and undergo a passive cool-down session in which they are seated in a chair. The participant's heart rate and blood pressure will be continuously monitored through the cool-down period and the participant will not be allowed to leave until the vital signs return to normal patterns. Blood pressure will also be monitored both before and after the fitness test to ensure that changes in blood pressure resulting from exercise are all normal. If the participants vital signs remain elevated after a cool down and rest period, the study physician will be called and will provide instructions for further monitoring of the participant. Situations like this are very rare and occur in less than 1/10,000 instances of fitness testing. These assessments will be conducted in [name] laboratory by an exercise physiologist with >15 years of coaching and exercise testing who is AED and Recertified and has certifications in exercise physiology from the American College of Sports Medicine. Prior to engaging in exercise, participants may be fitted with one or two physical activity monitoring devices (Body Media Sense Wear mini armband or Autographing). The Body Media Sense wear Armband is worn around the upper left arm. Hectograph Link is a wristband worn on the non-dominant arm. Both devices will record physiological data (e.g., heat flux, sweat rate, etc.) over the duration of their exercise test; this information is used in an algorithm to determine intensity and amount of physical activity. The participants will be provided with detailed instructions regarding wearing of the device(s) as well as the option to remove the device(s) if it becomes problematic. Participants may also be asked to wear the physical activity monitoring device(s) for a week before or after the exercise testing session. This way we can get a more comprehensive idea of both activity and fitness levels. In addition, all participants, regardless of group assignment, will be asked to wear the device(s) 3 additional times through their participation in this study(approximately every 5 weeks) and again at the follow-up assessment (TP2) for total of 5 times over the course of participation in the study. Participants who wear the Actigraphy Link will be given a log at the time they receive their device. This log is used to report any time/reason the device is removed as well as information about their sleep. The self-report information contained in the log will be compared to and used in interpreting the device data. Alternatively, in the event that a participant cannot come to Sennott Square for this testing for any reason (e.g., preference, weather, pandemic-related restrictions.), a brief heart-rate monitoring session may take place virtually either by phone or teleconferencing. During this guided session, the participant will be asked to wear study-provided heart rate monitor for approximately 5 minutes and asked to report readings to study staff. Participants will also be asked to report their weight; home scale may be provided for participants to use (with instructions to return via pre-paid mailer when complete). Data from the session can provide information to estimate results from a VO_2 test. Participants may also be asked to complete questionnaires regarding exercise knowledge and self-efficacy during the physical activity and fitness assessment, time permitting. Alternatively, these may be included in the behavioral assessment. The behavioral assessment includes a battery of standard clinical neuropsychological tests that assess verbal ability, visuospatial ability, attention/processing speed, memory, and executive function, will be administered. These tests have standard administration protocols and will be administered by trained staff. This is expected to take approximately 90 minutes. We will also administer measures of demographics, mood and quality of life. The tasks and measures will include those listed in section 2.8. All of the tests will be identified by the subject ID and not by name. At times these tests can be mentally fatiguing or frustrating. Subjects will be told that the tests are designed to be challenging and that they should just perform to the best of their abilities. They will also be offered breaks as needed between tests to help reduce fatigue and frustration. Data collected will be transported by the research personnel immediately following the assessment if conducted in the participant's home to the office of the PI in the

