Analysis Plan for Aim 1. An "intent-to-treat" (ITT) approach will be used for data analysis. All subjects will be included in the groups to which they were assigned, regardless of adherence to protocol, treatment received, withdrawal or protocol deviation. Although this approach is recommended for efficacy analyses in Retaste sensitivity of the results assuming ITT will be explored using information collected regarding participant's adherence to the exercise intervention (e.g., protocol, amount of treatment received) as well as the amount of activity engaged in by the usual care group. The primary endpoint, changes in cognitive function, will be derived from normed (for age, education) composites of neuropsychological test scores (expressed as mean Z-scores).¹ (Table 2) The composite scores for the targeted cognitive function domains are empirically derived via exploratory factor analysis. Given the variation in scaling, test scores are converted to Z-scores related to an established cohort of age- and education-matched healthy women, and then averaged into composites, where negative scores indicate poorer cognitive function. Linear mixed-effects modeling with linear contrasts will be used to examine the effect of treatment assignment on cognitive function over time. When fitting models, time will be repeated within-subjects

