factor, while treatment assignment will be a between-subjects factor, with an interaction between time and group. Each derived cognitive domain composite will be modeled separately and interaction terms will be included to test our hypothesis that executive, memory, and attention domains will be more affected than other domains. We will consider baseline cognitive function values both as an assessment point and as a possible covariate in analyses. Fixed and/or time-dependent covariates may be included to adjust for group imbalances or variables related to the dependent variables. Standard fit indices will also be used to identify the most appropriate covariance structure. F-tests will test the main and interaction effects included in the model. Individual regression parameters will be computed and reported with standard errors to yield confidence intervals. For each model, residual analysis will be conducted to identify sources of model misspecification, outliers and influential observations. Sensitivity analyses will be performed to discern the impact of influential cases on results. To test specific hypotheses, linear contrasts will be specified and estimated in the repeated measures model to compare changes from follow-up to baseline values between groups. Wald t-statistics will be used to test each contrast. Marginal modeling with generalized estimating equations will also be used as it tends to be more robust to misspecification of the covariance structure and violations in normality assumptions. Results from each modeling approach will be compared via sensitivity analyses.

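### The promised test that executive, memory and attention domains respond more than other domains cannot be run from the plan as written, because every Aim 1 model holds a single domain

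*Combined protocol and SAP*

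**What the plan says.** Under Specific aims, Hypothesis 1 makes two statements: exercise will improve cognitive function, and it will do so selectively, so that "attention, executive and memory functions will be influenced more than other domains".

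The Statistical Plan (Analysis Plan for Aim 1) takes the composites as the primary endpoint. It specifies a linear mixed model with time as the within-subject factor and treatment as the between-subject factor, "with an interaction between time and group". Of each composite it then states: "modeled separately and interaction terms will be included to test our hypothesis that executive, memory, and attention domains will be more affected than other domains". On testing, it says that "F-tests will test the main and interaction effects included in the model", and that "linear contrasts will be specified and estimated in the repeated measures model to compare changes from follow-up to baseline values between groups".

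On scale, "test scores are converted to Z-scores related to an established cohort of age- and education-matched healthy women". The Assessments text describes the battery as covering "verbal ability, visuospatial ability, attention/processing speed, memory, and executive function". The composites are said to come from exploratory factor analysis, with a reference to Table 2, and the list of measures is referred to section 2.8. Neither is in the text provided.

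**The concern.** A claim that one set of domains responds more than another concerns a difference between treatment effects, so its test needs those effects in one model or in one contrast with a known covariance. The plan assigns the test to interaction terms, but in the same sentence puts each domain in a model of its own.

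Without a stated between-domain contrast, the separate results can only be set side by side. A significant effect in one domain next to a non-significant effect in another does not show that the two effects differ. The way of comparing (which domains, which scale, which rule) could also be settled after the results are known. At stake is the comparative part of Hypothesis 1, not the effect within any one domain.

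**Working it through.** **Structural check.** No figure in the plan is available to reproduce: the text provided gives no alpha, effect size, SD, correlation or dropout for Aim 1. The argument rests on the model descriptions.

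1. Fixed effects named for Aim 1: time, group, time by group. Domain is not listed as a factor.
2. With one composite as outcome, domain is constant within the model, so a group by time by domain term cannot be estimated. Time by group asks whether that domain responds, not whether it responds more than another.
3. The F-tests cover effects in the fitted model, and the linear contrasts compare change between groups. Neither crosses domains.
4. The generalized estimating equations are added for robustness, with no domain factor. Aim 2 reuses the Aim 1 approach. Aim 3 adds E2 and its interactions to the Aim 1 models. None brings in a second domain.

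**Illustration of size.** Assumptions, none stated in the documents except the ceiling on arm size: n = 127 per arm (Participants says up to 127), no dropout, three targeted and two other composites, two-sided 0.05, effects in SD of change, equal correlation ρ of 0.3 to 0.7 between the domains' effect estimates.

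- One domain: SE = √(2/n) = √(2/127) = 0.1255.
- Joint contrast (mean of three minus mean of two): SE = 0.1255 × √[(1−ρ)(1/3 + 1/2)] = 0.0958, 0.0810 and 0.0627 at ρ = 0.3, 0.5 and 0.7.
- Power = Φ(δ/SE − 1.96), ignoring the far tail. For 0.35 versus 0.20 SD, δ = 0.15; at ρ = 0.3, 0.15/0.0958 = 1.565 and Φ(−0.395) = 35%.
- Pattern rates: integration over the shared normal factor of five equicorrelated estimates.

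| Quantity | ρ = 0.3 | ρ = 0.5 | ρ = 0.7 |
|---|---|---|---|
| Equal effects 0.20 SD: at least one targeted significant, no other | 23.6% | 19.1% | 14.1% |
| Equal effects 0.25 SD: same | 18.9% | 16.3% | 12.8% |
| Equal effects 0.40 SD: same | 2.3% | 3.0% | 3.3% |
| Equal effects 0.20 SD: all three targeted, neither other | 1.6% | 1.4% | 1.0% |
| Equal effects 0.25 SD: same | 2.2% | 1.7% | 1.2% |
| True 0.35 v 0 SD: all three targeted, neither other | 51.2% | 55.7% | 61.1% |
| True 0.35 v 0 SD: joint contrast | 95.5% | 99.1% | 100.0% |
| True 0.35 v 0.20 SD: joint contrast | 34.7% | 45.7% | 66.7% |
| Difference detectable with 80% power, joint contrast (2.80 × SE) | 0.27 SD | 0.23 SD | 0.18 SD |

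Under equal effects the joint contrast rejects in 5% of trials, 2.5% in the hypothesised direction.

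**Limit of the averaged contrast.** If one targeted domain gains 0.35 SD and the other four gain nothing, the contrast is 0.35/3 = 0.117 SD. It then rejects with probability Φ(0.117/SE − 1.96), which is 23%, 30% and 46% at ρ = 0.3, 0.5 and 0.7. Rejection therefore does not show that every targeted domain responds more.

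**The case against.** The strongest reply is that the sentence describes two steps: fit each domain separately, then add interaction terms for the domain hypothesis. The plan also says that contrasts will be specified for particular hypotheses. This reading is possible, so a reader who infers that the plan contradicts itself, or that no between-domain test was intended, goes further than the text allows. What stands is that the second step has no model, domain factor, cross-domain covariance or contrast, so two analysts could carry it out differently.

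Three other inferences also go too far:

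- **That Aim 1 or the whole of Hypothesis 1 is untestable.** Aim 1 asks whether exercise improves cognitive function. Time by group answers that within each domain.
- **That the trial carries a 13-24% false-positive rate.** That range belongs to a lenient rule which the plan does not state; its promise of interaction terms points away from such a rule. The rate drops to 2-3% at 0.40 SD. It also depends on the assumed split: at 0.20-0.25 SD it is 23-37% with one other domain and 6-12% with four. Under the strict rule, closer to a hypothesis naming three domains, false claims are rarer than the joint contrast's 5%; the cost of that rule is lost power.
- **That the composites or the domain grouping are undefined.** Table 2 and section 2.8 are outside the text provided and may define them. A list of composites would still not supply a joint model.

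**Conclusion.** The point holds in a limited form. The interaction test promised for the comparative part of Hypothesis 1 cannot be carried out with the models described under Aim 1, and the other aims' analysis plans do not fill the gap. This is more than missing detail, because the stated method of one domain per model cannot give the promised comparison. Analyses within each domain are unaffected.

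The conclusion is structural and does not depend on the illustrative figures, which show only what is lost if separate results are compared instead: either a loose rule that can mislead at modest effects, or a strict rule that misses roughly 39-49% of true 0.35 versus 0 SD patterns (100 − 61 and 100 − 51). They rest on assumed effect sizes, correlations, full arms and a three-versus-two split. The plan should be amended; the repair is inexpensive.

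**What to change.** Keep the separate models for the effect within each domain, and add wording such as:

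*The comparative part of Hypothesis 1 will be tested in one joint mixed model of all composites, with domain and time as within-subject factors and a covariance that allows different variances and correlation across domains and times. The test is the group by time by domain contrast: the mean group by time effect in the targeted composites minus the mean in the other composites. Because this averaged contrast can reject when only one targeted domain responds, each targeted domain's difference from the mean of the others will be reported with a confidence interval.*

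Before any comparison by group, fix:

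- which composites are targeted and which are other, citing Table 2 if it already says so;
- the scale on which effects count as equal, for example the normed Z units or each composite divided by its baseline SD. If effects equal on one scale differ by 0.10 SD on another, the contrast on that other scale rejects in 18-36% of trials (ρ = 0.7 gives Φ(0.10/0.0627 − 1.96) = 36%).

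**Cost.** SAP wording and one added model, with no new data. The covariance is larger: five composites at two times, unstructured, need 10 × 11/2 = 55 parameters, so a simpler fallback structure should be named. Power is limited if the other domains also improve (35-67% for 0.35 versus 0.20 SD). The single-domain differences are less precise: SE = 0.1255 × √[1.5(1−ρ)], giving 95% half-widths of 0.25, 0.21 and 0.16 SD at ρ = 0.3, 0.5 and 0.7.

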1. Postmenopausal women, defined by lack of a menstrual period for an entire year or confirmed by physician 2. 18-80 years of age 3. Able to speak and read English 4. Completed a minimum of 8 years of education 5. Diagnosed with stage 0, I, II, or IIIa breast cancer, confirmed by medical record 6. Within 2 years post-completion of primary treatment 7. Will be at least two weeks post-breast conserving surgery or three weeks post-breast conserving surgery with sentinel lymph node biopsy or four weeks post-mastectomy at the start of participation.

Exclusion criteria:

1. Prior treatment with cancer chemotherapy, central nervous system radiation, or intrathecal therapy 2. Prior cancer involving the central nervous system 3. Clinical evidence of metastatic disease 4. Any of the following breast cancer surgery complications unless approved by the participant's health care provider: persistent seroma requiring aspiration, wound dehiscence, infection, prolonged drain output, lymphedema 5. Reconstructive surgery unless approved by the participant's health care provider 6. Any significant medical condition that would preclude them from exercising (e.g., uncontrolled diabetes, congestive heart failure, angina, uncontrolled arrhythmia or other symptoms that indicate increased risk for an acute cardiovascular or

Research activities:

Participants: We plan to recruit up to 350 postmenopausal women with early-stage breast cancer: up to 127 will undergo an exercise intervention in this 6-month study described below and up to 127 will be enrolled in an usual care arm. A subsample of women who are randomized will participate in the neuroimaging component of the study (n=150; 75/group).

Locations: Recruitment will take place at St. Clair Budway Surgical Associates and Magee-Women's Hospital of UPMC, Comprehensive Breast Care Center at UPMC Passavant-Cranberry, UPMC South Hills, UPMC McKeesport and Magee Woman care Center in Monroeville. Data collection will take place in participants' homes, at the University of Pittsburgh School of Nursing and Sennott Square or Healthy Lifestyle Institute offices in Oak Hill. The exercise intervention will take place at Sennott Square, Baierl Family YMCA, Sampson Family YMCA, and JCC South Hills Branch or Healthy Lifestyle Institute offices in Oak Hill; alternatively, a participant may exercise in her home or other location of her choosing. MRI Imaging will take place at Carnegie Mellon University SIBR.

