Informed Consent: Written informed consent will be obtained from the participant prior to any study-specific activities either in person or remotely.

Assessments: Participants will complete a series of assessments at two timepoints; Time 1(baseline) will occur up to 2 years post-completion of primary treatment and before randomization and initiation of the exercise intervention/usual care. Time 2 will occur approximately within 1 month of completion of the intervention (or 7 months post-Time 1). Data collection at each timepoint will be composed of behavioral assessments, blood samples, neuroimaging and objective measures of physical activity and fitness. We will also objectively evaluate physical activity at 3 time points during participation (approximately every 5 weeks). For participants who agree to additional follow-up via the addendum consent form, Time 3 will take place approximately 6 months post Time 2 and will consist of blood work, fitness testing and behavioral testing as described below. We will also objectively evaluate physical activity at midway (3 months) between Time 2 and Time 3 as well as at Time 3. Participants will also be asked to maintain their edema cap and REDCap diaries during this time. Participants may be asked to complete assessments in two separate sessions at both TP1 and TP2. During one visit (which includes fitness testing), blood samples (approximately 30cc or 6 teaspoons) will be collected for biobanking for future evaluation of the relationships of biomarkers (including genetic biomarkers) with cognitive function, exercise, brain health and symptoms. Blood samples will be transported immediately, under conditions appropriate for preservation of the blood, and stored before the end of the day of testing. Samples will be maintained in a -80°C freezer in the Victoria building under the control of the principal investigators of this research project and will be maintained indefinitely. In the event that we need to send samples to a different facility outside of the University of Pittsburgh for analysis in the future, no identifying information will accompany the sample. Participants will be asked questions prior to the blood draw to determine any factors which may affect the findings. If a recent illness is noted, or certain other factors as noted on the form, are found, the participant may not be eligible for a blood draw at this visit. In this event, we will attempt to collect the blood at another time, either during a subsequent visit or other agreed upon time. Fitness will be objectively measured at Time 1 and Time 2. This test takes 15-30 minutes to complete. Subjects will be given exercise testing instructions regarding proper clothing and footwear and will be told to abstain from caffeine or nicotine 2 hours prior to the physical activity/fitness assessment. When participants report to the laboratory (Sennott Square) for the fitness assessment they will first be acquainted with the equipment, allowed to ask any questions, and get comfortable with walking on a treadmill. Before the test begins, the participant will get familiar with wearing the mouthpiece and nose clips or facemask required during the test in order to measure cardiovascular fitness. This helps to reduce anxiety associated with exercise and fitness testing. Cardiovascular fitness testing consists of progressively increasing exercise intensity while the subjects exhaled air is collected via a mouthpiece that is connected to a gas exchange chamber via a breathing tube. A comfort fitted head gear supports the mouthpiece. This reduces the effort of the participant to keep the mouthpiece in the correct position throughout the test. Alternatively, the participant may wear a facemask. The gas chamber that is being used is the Parvo Medics True one 2400 metabolic cart, which is one of the most widely accepted systems in scientific research. Next we will provide the participant with adequate warm-up and stretching which will be monitored by the exercise physiologist. After 5-10 minutes of warm-up, the participant will walk on a motor-driven treadmill at a constant speed with increasing increments of the incline. We will conduct a submaximal vo_2 fitness test which estimates the maximal oxygen capacity for the individual without reaching an exhaustive level. The sub-maximal graded exercise test is a modified Balke protocol in which the speed remains constant and grade is increased 1% each minute. This protocol has been used extensively in the literature for fitness training for both normal, at-risk, and impaired populations. Verifying maximal vo_2 is difficult in at-risk

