
person exercise, as described above, will be the preferred method for intervention delivery. However, participants may also exercise at their home, or other location of their choosing, as needed. When exercising at home, participants will be in contact with a study trainer at least weekly. Participants will receive guidance and coaching related to their exercise sessions - either in real-time or other time as to be accommodating as possible to the research participants. Heart rate during exercise sessions will be monitored via study-provided monitors and will be reported to trainers by the participant. Participants may be provided with online resources/videos for exercise (such as Be Fit Pitt) or may be encouraged to use an exercise resources available to them (such as owned exercise equipment, gym memberships, indoor or outdoor walking, etc.)

Usual Care Group: will not withhold physical activity or limit physical activity in the usual care group but instead will let them engage in activity in the same manner as if they were not part of an active intervention.

Statistical Plan

Randomization: Subjects will be randomly assigned via a computer using a minimization algorithm with equal allocation to one of two treatment groups: 1) exercise intervention, or 2) usual care. Use of a minimization algorithm will insure treatment balance on two factors: 1) age at study entry (<60, >60 to <70, >70 years) (since age is associated with reduced fitness, cognition, and brain measures), and 2) baseline levels of cognitive function, particularly executive function (based on the composite mean Z-score, < -0.5, > -0.5 to < +0.5, > +0.5). Minimization is a form of adaptive treatment allocation in which the probability of assignment to the treatment groups does not remain constant but is determined by the current balance and/or composition of groups. In this study, the treatment assignment probability will be adjusted in response to the marginal distributions of categories of age at entry and baseline executive function such that the marginal distributions of these categories will be approximately equal between treatment groups. Treatment group assignment will be generated and stored in a secured database.

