Data analysis: Preliminary Analyses. Exploratory analyses will be performed for data description and screening for anomalies (e.g., outliers, nonnormality). This will be done to: 1) describe univariate and bivariate distributions; 2) identify group imbalances and associations between dependent variables and suspected covariates/ confounders; 3) evaluate missing data; and 4) check for violation of statistical assumptions. If assumptions are violated, data transformations or more statistically robust procedures will be considered. Covariates/ confounders will be included in models secondarily and their effects on primary predictors/factors will be evaluated. The randomness of missing data will be investigated using available information on subject characteristics to help discern patterns in missing data, identify possible missing data mechanisms and inform strategies to handle missing data. If the data are ignorable missing, the estimation procedures to be used will produce unbiased estimates while allowing us to retain observations with missing values on the outcome variables. If needed, multiple imputation would be used to impute missing values on covariates. If the data are not ignorable missing, we may use selection or pattern mixture modeling to investigate the sensitivity of results.

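### The role of the baseline score in the primary Aim 1 test is not fixed; an unadjusted change contrast would be valid but less powerful than a baseline-adjusted test, and probably conservative for executive function

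*Combined protocol and SAP*

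**What the plan says.** The Analysis Plan for Aim 1 fits a linear mixed model to each cognitive composite. Time is the within-subject factor and "treatment assignment will be a between-subjects factor, with an interaction between time and group". For the specific hypotheses, "linear contrasts will be specified and estimated in the repeated measures model to compare changes from follow-up to baseline values between groups", each tested by a Wald t-statistic. The same section names F-tests, interaction terms for domain specificity, and a GEE comparison as a sensitivity analysis.

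On the TP1 score it says: "We will consider baseline cognitive function values both as an assessment point and as a possible covariate in analyses". The Preliminary Analyses paragraph says of covariates in general: "Covariates/ confounders will be included in models secondarily and their effects on primary predictors/factors will be evaluated".

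Both Randomization paragraphs, under Research activities and in the Statistical Plan, balance the arms by minimization on "baseline levels of cognitive function, particularly executive function", banded at −0.5 and +0.5. Executive function is also an outcome, since Hypothesis 1 predicts that "attention, executive and memory functions will be influenced more than other domains". TP1 is measured "before randomization and initiation of the exercise intervention/usual care".

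**The concern.** The TP1 score of each domain is likely to be the strongest predictor of its TP2 score, and it is known for every woman before allocation. A plain change contrast gives TP1 a weight of exactly 1. When the TP1–TP2 correlation is moderate, that over-corrects and adds noise. Baseline adjustment uses the weight that the data support.

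Executive function has a further feature. Minimization has already removed most of the chance imbalance in its TP1 score, but the standard error of the unadjusted contrast is computed as if that imbalance were still present. The reported standard error is then too large and the test rejects too rarely. At stake is the chance of detecting a real effect, including in one of the three domains that Hypothesis 1 singles out.

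**Working it through.** **Inputs.** From the documents: equal allocation; a ceiling of 127 per arm ("up to 127 will be enrolled in an usual care arm", with the same ceiling for exercise); three executive-function bands. The documents give no alpha, effect size, SD or TP1–TP2 correlation r for Aim 1, so there is no stated power to reproduce. Assumed: two-sided 5%, SD 1 at both times, effect 0.25 SD, r from 0.5 to 0.9, complete TP1 and TP2 data.

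**Step 1: power.** With complete data the unadjusted contrast is the difference in mean change scores. With n per arm:

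- SE of the change contrast = √(4(1−r)/n)
- SE of the baseline-adjusted contrast = √(2(1−r²)/n)
- ratio of the two = √(2/(1+r))

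At r = 0.5 and n = 127, these are √(2/127) = 0.1255 and √(1.5/127) = 0.1087. The effect of 0.25 is then 1.99 and 2.30 standard errors. Power is from the noncentral t distribution.

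| r | SE change | SE adjusted | Ratio | Power, change | Power, adjusted |
|---|---|---|---|---|---|
| 0.5 | 0.1255 | 0.1087 | 1.155 | 51% | 63% |
| 0.7 | 0.0972 | 0.0896 | 1.085 | 73% | 79% |
| 0.8 | 0.0794 | 0.0753 | 1.054 | 88% | 91% |
| 0.9 | 0.0561 | 0.0547 | 1.026 | 99% | 99% |

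With an assumed 102 per arm, power goes from 43% to 54% at r = 0.5, from 63% to 70% at 0.7, and stays at 98% at 0.9.

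**Step 2: conservatism for executive function.** Let R² be the share of TP1 executive variance explained by the three bands; it is about 0.80 for a normal score with SD 1. If minimization balances the bands, then in common units:

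- variance that the model assumes = 2(1−r)
- actual variance = (1−r²) + (1−r)²(1−R²)

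At r = 0.5 these are 1.000 and 0.75 + 0.25 × 0.20 = 0.800. The reported SE is too large by √(1.000/0.800) = 1.118, the effective critical value is 1.96 × 1.118 = 2.19, and the type I error is 2.8%. At r = 0.7 the variances are 0.600 and 0.528, giving 3.7%. At r = 0.9 they are 0.200 and 0.192, giving 4.5%.

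Simulated minimization of 254 women on age and executive bands (assumed biased coin 0.8, 20,000 runs per setting) gave 2.9%, 3.6% and 4.4% unadjusted, and 4.8–5.0% adjusted. Moving the coin between 0.7 and 0.9 gave 2.7–3.0%, 3.5–4.1% and 4.3–4.7%. Under simple randomization the unadjusted rate was 4.8–5.1%, so the balancing is the cause.

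**Step 3: if the composites differ.** If the score used for allocation correlates c with the score analysed, R² is replaced by c²R². At c = 0.8 that is 0.64 × 0.80 = 0.512, and the type I error becomes 3.6%, 4.1% and 4.7% at r = 0.5, 0.7 and 0.9.

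**Step 4: is this a second power loss?** No. For executive function the simulated true SE of the change contrast exceeds that of the adjusted one by only 3.6%, 1.9% and 0.8% at r = 0.5, 0.7 and 0.9. The loss comes mainly through the overstated SE, and simulated power (51% to 63%, 73% to 79%, 99% to 99%) is about the same as in Step 1.

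**The case against.** The plan does not rule out baseline adjustment. Its sentence on TP1 leaves room for both remedies: TP1 as a covariate (ANCOVA) and TP1 as a response (a common-baseline model). If either is the primary test, the concern disappears. This stands, and it is why the point is conditional. What is missing is a commitment.

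Several stronger readings are tempting but unsupported:

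- **That the change contrast is the only test named.** F-tests, domain interaction terms and GEE are named too. With two time points and complete data, the group-by-time F-test is the square of this contrast and an unconstrained GEE targets the same difference, so they do not remove the issue. The comparison between domains is a separate question, not assessed here.
- **That TP1 is relegated to secondary models.** The Preliminary Analyses sentence concerns covariates in general, while the Aim 1 section treats baseline cognition separately. Applying the former to TP1 is an inference.
- **That false positives will be inflated.** Neither analysis alone does this. Taking the smaller of the two p-values would (about 5.5–7.4% in other domains, 5.1–5.4% for executive function, in simulation), but nothing says that the analysis will be chosen that way.
- **That executive function is certainly affected as calculated.** Analysis composites come from factor analysis, and the documents do not say that the allocation score is the same composite. A mismatch weakens the conservatism but leaves the power loss in place.

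The correlation is also unknown, and nothing in the documents favours 0.5 over 0.8.

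**Conclusion.** The point holds as a matter of efficiency and pre-specification. An unadjusted change contrast as the primary test would be valid and would match the stated endpoint. Under the assumptions above it would cost about 12 percentage points of power at r = 0.5, 6 at 0.7, 3 at 0.8 and essentially none at 0.9. For executive function it would also be conservative: about 3% at r = 0.5, 3.5–4.5% at 0.7 and 4.5% at 0.9 against a nominal 5%, provided that the allocation and analysis composites coincide. Effect size, SDs, correlation, coin probability and completeness are all assumed, and 127 per arm is a ceiling. The documents do not show bias, an invalid test, or a decision against adjustment. The change is worth making because the remedy is cheap and uses data already planned.

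**What to change.** State in advance that the primary Aim 1 analysis of each domain is baseline-adjusted.

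- **Preferred:** a longitudinal mixed model with TP1 as a response, the baseline mean constrained equal between groups, and unstructured covariance. The treatment effect is still a between-group difference in change. Women without TP2 stay in the analysis, in line with the all-subjects intention-to-treat rule.
- **Alternative:** ANCOVA of TP2 on the same domain's TP1, with a stated method for missing TP2 values. A plain ANCOVA would drop those women.
- **Minimization factors:** include those actually used (with time interactions in the longitudinal model). First reconcile the Randomization paragraph under Research activities, which lists three, with the one in the Statistical Plan, which lists two.
- **Executive function as outcome:** use its TP1 score once, as response or covariate, and do not also enter the executive band. State whether the allocation composite is the one analysed.
- **Sensitivity:** keep the unadjusted change contrast as a named sensitivity analysis.

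The cost is SAP wording, a check of the allocation database and a little more analysis work, with no new data collection. The gain is small if the TP1–TP2 correlation is 0.8 or more.
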